6.3 End of Treatment (or latest at Week 12, Month 3)

This assessment will be performed at end of treatment or latest at week 12. Procedures will be completed in the following order:

- The investigator will collect the paper diary card and transcribe the information recorded by the patient into the eCRF. The paper diary card will be stored with the patient's medical record.
- The investigator will assess and record any adverse events that occurred since the last visit.
- The investigator will record any concomitant use of IC/BPS medication, pain medication, and other relevant concomitant medication that were taken since the last visit; it is not required to collect all concomitant medication.
- Patients will be asked to complete the Bladder Pain/Interstitial Cystitis Symptom Score (BPIC-SS).
- Patients will be asked to complete the Patient Global Assessment (PGA).
- Patients will be asked to complete the Visual Analogue Scale (VAS) for bladder pain, urinary urgency, and quality of life (QoL).
- Cystistat will be instilled into the bladder according to the instructions for use.
- The investigator will provide the patient with the diary card and instruct her on how to record study related data at home. The following assessments are to be filled out by the patient:
 1. Morning voiding volume (once at month 6)
 2. Urinary voids and the respective volumes over a period of 24 hours (once at month 6)
 3. Use of concomitant IC/BPS medication, pain medication, and other relevant concomitant medication
 4. Adverse events

- The investigator will assess and record any adverse events and incidents, including any related adverse events, use error, and malfunction (see "incident" definition, [Section 10.1](#)), that occurred until or during this visit. All adverse events and incidents must be transmitted to the sponsor via the eCRF (see [Section 10.4.1](#) for reporting requirements).

Special focus will be posed on the side effects listed in the instructions for use of the investigational device: allergic reaction (local rash and/or itching), bladder/urethral pain and discomfort, or urinary tract infection.

- The investigator will enter all required data from this visit in the eCRF within 5 business days. Specific reporting requirements for AEs and incidents are described in [Section 10.4.1](#).
- If required, treatment with Cystistat will be continued thereafter under regular medical care. For all patients, a follow-up visit will be scheduled for approximately month 6.

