6.4 Follow up (approximately at Month 6)

Follow-up will be performed as an on-site visit if in accordance with routine clinical practice; if not possible as an on-site visit, the information will be collected remotely (e.g., via phone and postal mail) from the patient.

Procedures will be completed in the following order:

- The investigator will collect the paper diary card and transcribe the information recorded by the patient into the eCRF. The paper diary card will be stored with the patient's medical record.
- The investigator will assess and record any adverse events that occurred since the last visit.
- The investigator will record any concomitant use of IC/BPS medication, pain medication, and other relevant concomitant medication that were taken since the last visit; it is not required to collect all concomitant medication.
- Patients will be asked to complete the Bladder Pain/Interstitial Cystitis Symptom Score (BPIC-SS).
- Patients will be asked to complete the Patient Global Assessment (PGA).
- Patients will be asked to complete the Visual Analogue Scale (VAS) for pain.
- The investigator will assess and record any adverse events and incidents, including any related adverse events, use error, and malfunction (see "incident" definition, [Section 10.1](#)), that occurred until or during this visit. All adverse events and incidents must be transmitted to the sponsor via the eCRF (see [Section 10.4.1](#) for reporting requirements).

Special focus will be posed on the side effects listed in the instructions for use of the investigational device: allergic reaction (local rash and/ or itching), bladder/urethral pain and discomfort, or urinary tract infection.

- The investigator will enter all required data from this visit in the eCRF within 5 business days. Specific reporting requirements for AEs and incidents are described in [Section 10.4.1](#).

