7.1.3.1 Bladder Pain

Patients will be asked to assess their bladder pain on the VAS using the question “How was your bladder pain over the last 3 days?”. The VAS will be an unmarked line ranging from 0 to 100 mm, where 0 = “no pain” and 100 = “worst possible pain”.

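### The prescribed visit order places the patient-rated PGA, BPIC-SS and VAS after the investigator's diary, adverse-event and medication review, and no remote route is assigned per instrument at month 6

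*Protocol*

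**What the plan says.** Protocol section 6.3 governs the visit at which the primary endpoint is taken: "Procedures will be completed in the following order". Three investigator steps come first:

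1. "The investigator will collect the paper diary card and transcribe the information recorded by the patient into the eCRF"
2. "The investigator will assess and record any adverse events that occurred since the last visit"
3. "The investigator will record any concomitant use of IC/BPS medication, pain medication, and other relevant concomitant medication that were taken since the last visit"

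The patient then completes the BPIC-SS, the PGA and the VAS, in that sequence, and the instillation follows. Section 6.4 (month 6) also prescribes an order and puts the same three investigator steps before the same questionnaires. Section 6.5 (withdrawal and early termination) lists diary and adverse events first but fixes no order.

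When a month-6 visit on site is not possible, "the information will be collected remotely (e.g., via phone and postal mail) from the patient". The Table 0-1 footnote, section 4.2.3 and SAP section 4.8 carry the same provision. For bladder pain, section 7.1.3.1 says "The VAS will be an unmarked line ranging from 0 to 100 mm". Sections 7.1.3.2 and 7.1.3.3 use the same format for urgency and quality of life. Sections 7.1.1 to 7.1.3 have the patient complete each instrument and site staff transfer the data. Section 9.13 describes the questionnaires as paper-based.

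**The concern.** The primary endpoint is one subjective rating. The study has one treatment group and no blinding (SAP sections 4.4 and 5.3), so an effect of the preceding conversation cannot be separated from an effect of treatment. The conversation is held by the treating investigator and covers ground that the PGA asks about. Flares are defined as symptom deterioration and recorded as adverse events (Protocol section 7.1.7), and the medication step covers IC/BPS and pain drugs.

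The responder rule adds a sensitive spot. A patient who reports slight improvement counts as a responder only if she also answers yes to a question about positive effect and willingness to repeat the treatment (section 7.1.1). In section 6.3 she would answer it after the review and shortly before the next instillation.

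At month 6 the stake is smaller. If a remote contact were made by phone alone, the VAS could not be completed in the form used at baseline, and the change from baseline in pain, urgency or quality of life would then combine two ways of measuring.

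**Working it through.** The main check is a comparison of texts. Arithmetic serves only to show scale.

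**Order**

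| Place | Order prescribed? | Investigator steps listed before the questionnaires |
|---|---|---|
| Protocol 6.3, end of treatment or week 12 | Yes | Diary, adverse events, medication |
| Protocol 6.4, month 6 | Yes | Diary, adverse events, medication |
| Protocol 6.5, early termination | No | Diary and adverse events listed first; no medication step |

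Sections 7.1.1 to 7.1.3 and 9.13 establish who completes the forms and on what medium. None of them requires completion before the investigator's review, or in private. The stated order in 6.3 and 6.4 therefore stands unqualified.

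**Mode at month 6**

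- Routes: phone and postal mail are both named, as examples. Section 10 also mentions contact by mail or e-mail. No route is assigned to an instrument.
- Materials: in section 6.3 the only item handed out for month 6 is the diary card. Its four listed contents are morning voiding volume, 24-hour voids with volumes, medication and adverse events. No PGA, BPIC-SS or VAS form is among them, and no step sends such forms to a remote patient.
- Analysis: SAP sections 7.1 to 7.3 describe no mode variable and no analysis by mode.
- Scope: the remote option is written for month 6 only.

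**Scale**

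- Inputs: total 74, of which 7 allow for about 10% drop-out (Protocol 8.1, SAP 5.1). The derivation of the base number is redacted; by subtraction it is 74 − 7 = 67.
- The plan's own figure: 67 × 1.10 = 73.7, rounded up to 74, which matches. Dividing instead, 67 / 0.90 = 74.4, gives 75.
- One patient changing responder status: 1/67 = 1.5 points, or 1/74 = 1.4 points if the FAS contains all 74.
- Sampling error for comparison: the SAP plans a 90% interval whose method is redacted. A Wald half-width, 1.645 × √(p(1 − p)/67), is assumed here, with p set at the 60% and 85% ends of the remission range cited in Protocol 1.2:
  - p = 0.60: 1.645 × √(0.24/67) = 9.8 points
  - p = 0.85: 1.645 × √(0.1275/67) = 7.2 points

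The interval reflects sampling error only and would not include an order effect. How many patients, if any, would rate differently after the review cannot be derived from the documents.

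**The case against.** On the order, the other side has four arguments.

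- The listed steps are transcription and recording, not a formal symptom interview.
- The questionnaires already precede that visit's instillation.
- Patients may have had the same review at up to 11 weekly visits (section 6.2), so moving the forms forward at one visit removes only part of the investigator's influence.
- Talk of side effects could lower a rating as easily as raise it, and all analyses are declared exploratory.

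These limit what can be claimed about size and direction. They do not give a reason for the present order, and the conversation immediately before the rating is the part that the protocol can remove at almost no cost.

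On month 6, a reader might infer that remote VAS values are spoken numbers pooled with marked ones. The documents do not support that. Postal mail is named alongside the phone, the questionnaires are paper-based and patient-completed, and the paper diary card has to be returned anyway, so a VAS sheet could travel with it. No text says that any VAS is taken orally. Nor can it be said that the mode goes unrecorded, because the eCRF design cited in the SAP is not among the documents. What stands is that the route per instrument is left open and that no step supplies the forms.

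**Conclusion.** The point holds in two parts of unequal weight.

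The first part is firm. Sections 6.3 and 6.4 prescribe that the patient-rated outcomes, including the primary PGA, follow the treating investigator's review. In an unblinded single-arm study this is an avoidable route of bias. Its size and direction are unknown, and the figure of 1.5 points per patient gives scale, not an estimate. It does not support a claim that the responder rate is inflated, and it does not invalidate the study.

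The second part is a gap in specification at month 6 that touches secondary endpoints only. A reader might extend it to the primary PGA, but the remote option is not written for the end-of-treatment or week-12 assessment. It matters only if some month-6 contacts are made by phone alone; the documents neither prescribe nor exclude that and give no expected share.

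**What to change.** 1. In sections 6.3 and 6.4, make the PGA, BPIC-SS and VAS the first steps, self-completed by the patient before any discussion of diary, adverse events or medication. Arrange the 6.5 list the same way for consistency.
2. In section 6.3, add month-6 paper copies of the three instruments, with the VAS line printed at 100 mm and a return envelope, to the diary card handed out. State in 6.4 that a remote patient completes them on paper and returns them by post, and that the phone serves for adverse events, medication and reminders.
3. Record the month-6 collection mode and add a tabulation of month-6 results by mode to the SAP.
4. While editing 6.4, reconcile its VAS item, which names pain only, with Table 0-1 and the secondary endpoints, which require pain, urgency and quality of life.

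The cost is a re-ordering of existing steps, some printing and postage, and one eCRF field if none exists. No visit is added. The drawback is that postal returns may arrive late or not at all.

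The protocol planned the study to end in Q3 2023 and the SAP is dated 30 November 2023, so data collection may be over. In that case, recover the mode from source records where possible, tabulate month 6 by it, and report the visit order as a limitation of the primary result.

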6.4 Follow up (approximately at Month 6)

Follow-up will be performed as an on-site visit if in accordance with routine clinical practice; if not possible as an on-site visit, the information will be collected remotely (e.g., via phone and postal mail) from the patient.

Procedures will be completed in the following order:

- The investigator will collect the paper diary card and transcribe the information recorded by the patient into the eCRF. The paper diary card will be stored with the patient's medical record.
- The investigator will assess and record any adverse events that occurred since the last visit.
- The investigator will record any concomitant use of IC/BPS medication, pain medication, and other relevant concomitant medication that were taken since the last visit; it is not required to collect all concomitant medication.
- Patients will be asked to complete the Bladder Pain/Interstitial Cystitis Symptom Score (BPIC-SS).
- Patients will be asked to complete the Patient Global Assessment (PGA).
- Patients will be asked to complete the Visual Analogue Scale (VAS) for pain.
- The investigator will assess and record any adverse events and incidents, including any related adverse events, use error, and malfunction (see "incident" definition, [Section 10.1](#)), that occurred until or during this visit. All adverse events and incidents must be transmitted to the sponsor via the eCRF (see [Section 10.4.1](#) for reporting requirements).

Special focus will be posed on the side effects listed in the instructions for use of the investigational device: allergic reaction (local rash and/ or itching), bladder/urethral pain and discomfort, or urinary tract infection.

- The investigator will enter all required data from this visit in the eCRF within 5 business days. Specific reporting requirements for AEs and incidents are described in [Section 10.4.1](#).

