- Diagnostic criteria of IC/BPS diagnosis
- Previous and current treatments

⁵⁾ Patient Global Assessment of overall IC/BPS condition improvement: To be completed at end of treatment or latest at week 12 and at month 6.

⁶⁾ Bladder Pain/ Interstitial Cystitis Symptom Score (BPIC-SS): To be completed prior to the first treatment, at end of treatment or latest at week 12, and at month 6.

⁷⁾ Visual Analogue Scale (VAS) for bladder pain, urinary urgency, and quality of life (QoL): To be completed prior to first treatment, at end of treatment or latest at week 12, and at month 6.

⁸⁾ Instillation of Cystistat: Cystistat will be instilled into the bladder according to the instructions for use; the regimen and duration of treatment will depend on the investigators' discretion; each instillation of Cystistat until month 6 will be recorded in the eCRF; the observation period for this study will end approximately at month 6 (irrespective of the duration of treatment); if required, treatment will be continued after month 6 under regular medical care.

⁹⁾ Diary card: The following assessments are to be filled out by the patient:

- Morning voiding volume once a week, preferably on the treatment day (until end of treatment or latest week 12) and once at month 6
- Urinary voids and the respective volumes over a period of 24 hours once a week, preferably starting the day before the treatment day (until end of treatment or latest week 12) and once at month 6
- Use of concomitant IC/BPS medication, pain medication, and other relevant concomitant medication (until month 6)
- Adverse events (until month 6)

¹⁰⁾ The use of concomitant IC/BPS medication, pain medication, and other relevant concomitant medication will be recorded; it is not required to collect all concomitant medication

¹¹⁾ Adverse events and incidents will be recorded after first instillation of Cystistat; prior to first instillation of Cystistat only adverse events will be recorded.

SIGNATURE PAGE

Protocol Title Real-world evidence observational study to evaluate performance and safety of intravesical sodium hyaluronate (Cystistat®) in the treatment of patients with interstitial cystitis (IC)/bladder pain syndrome (BPS)

Protocol Number CYST-SLZ-7001

Version 1.0

Protocol Date 06-Apr-2022

Clinical Sciences Lead (Author):

[REDACTED] [REDACTED] [REDACTED]
[REDACTED] Urology, Allergy
Global Clinical Sciences

Safety Lead (Reviewer):

[REDACTED] [REDACTED] [REDACTED]
[REDACTED] Global Parapharmaceutical

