2.2.2 Secondary Endpoints

The secondary endpoints of the study are:

- Morning voiding volume over time (from patient diaries, until month 6).
- Total number of voids and total voiding volume (daytime and nighttime) over the last 24 hours (from patient diaries, until month 6)
- Change from baseline to end of treatment or latest to week 12 and to month 6 in Bladder Pain/Interstitial Cystitis Symptom Score (BPIC-SS).
- Percent responders at month 6 as indicated by improvement on the 7-point Patient Global Assessment (PGA) scale using the same responder definition as for the primary endpoint.
- Percent responders at end of treatment or latest at week 12 and at month 6 as indicated by improvement on the 7-point Patient Global Assessment (PGA) scale using an alternative responder definition (i.e. a responder is defined as a patient who experiences moderate or marked improvement).

- Change from baseline to end of treatment or latest to week 12 and to month 6 in bladder pain and urinary urgency on Visual Analogue Scale (VAS) scored from 0 to 100.
- Change from baseline to end of treatment or latest to week 12 and to month 6 in quality of life (QoL) on Visual Analogue Scale (VAS) scored from 0 to 100.
- Use of concomitant IC/BPS and pain medication count (until month 6).
- Occurrence of flares (documented as adverse events) and additional BPIC-SS (at the time of occurrence) (until month 6).
- Premature termination of treatment.
- Safety assessments: Adverse events and incidents (until month 6).

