6 STUDY CONDUCT

When the clinical decision has been made to prescribe Cystistat for the first time to a patient according to the instructions for use (13), the investigator will consider enrolling the patient into this NIS. The decision to prescribe Cystistat must be previous and independent from the decision to include the patient in the NIS.

Patients eligible for study recruitment will have the nature, purpose, and risks of the study explained to them by the investigator. They will be provided with a written copy of the informed consent form (ICF) for the study and given sufficient time to consider the study's implications before deciding to participate. Patients agreeing to participate in the study will sign the ICF and be given a duplicate copy before recording any personal data.

In cases where the patient does not return to the next routine treatment, the site should make every effort to contact the patient so that they can appropriately be withdrawn from the study. All contact attempts should be documented in the patient's medical record. Should the patient continue to be unreachable, then she will be considered to have withdrawn from the study as "Lost to Follow-up." For all other patients withdrawing from the study, an alternative reason for discontinuation should be recorded in the eCRF. Patients may voluntarily withdraw from the trial for any reason and at any time.

In this NIS, the intended duration of observation per patient is approximately 6 months after start of treatment (irrespective of the duration of treatment). For details and timings of assessments, refer to [Section 7.0](#) and [Table 0-1](#).

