7.1.3 Visual Analogue Scale (VAS)

The VAS will be provided to assess disease-related symptom severity and general quality of life (QoL). It has been widely used in clinical studies with the indication IC/BPS (e.g. 8, 16, 17).

The related question for the VAS will be provided in local language. It will be completed by the patient at baseline, at the end of treatment or latest at week 12, and at month 6. Data will be transferred into the eCRF by the site staff.

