7.1.3.2 Urinary Urgency

Patients will be asked to assess their urinary urgency on the VAS using the question “How intense was urinary urgency over the last 3 days?”. The VAS will be an unmarked line ranging from 0 to 100 mm, where 0 = “no urgency” and 100 = “worst possible urgency”.

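### The month-6 visit list in Protocol 6.4 asks only for the pain VAS, while the schedule, the endpoints and the SAP also need urgency and quality of life

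*Protocol*

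**What the plan says.** Section 6.4 sets out the month-6 procedures in order and, for the VAS, says only: "Patients will be asked to complete the Visual Analogue Scale (VAS) for pain". It allows the visit to be done remotely, by phone and post.

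The rest of the plan asks for more at that visit:

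- Table 0-1 footnote 7 covers all three scales and gives their timing: "quality of life (QoL): To be completed prior to first treatment, at end of treatment or latest at week 12, and at month 6". SAP 4.8 repeats the footnote.
- Protocol 7.1.3, the parent section of the pain, urgency and QoL scales, does not limit month 6 to pain: "It will be completed by the patient at baseline, at the end of treatment or latest at week 12, and at month 6".
- Protocol 2.2.2 makes month-6 change a secondary endpoint for urgency ("to month 6 in bladder pain and urinary urgency on Visual Analogue Scale (VAS) scored from 0 to 100") and for QoL ("to month 6 in quality of life (QoL) on Visual Analogue Scale (VAS) scored from 0 to 100").
- Protocol 8.3.6 plans an ANCOVA of month-6 change for all three scales. SAP 7.2 takes separate week-12 and month-6 effects from one mixed model for each scale.

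The parallel procedure lists in 6.1 (baseline), 6.3 (end of treatment) and 6.5 (early termination) each name the three scales.

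**The concern.** Section 6.4 is the list a site would work through at month 6, and it is the only VAS visit list that names fewer than three scales. Remote follow-up is the most plausible setting for trouble, because a site may assemble its phone script or postal pack from that list.

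A missed value cannot be repaired later. The urgency question is "How intense was urinary urgency over the last 3 days", and the QoL question uses the same three-day window, so a query weeks afterwards cannot recover a month-6 answer. SAP 5.11 analyses observed data only, without imputation. Any loss would also cluster by site, so it might not be random with respect to outcome.

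The protocol text was not corrected. SAP 2.3 and 2.4 (SAP version 1.0, 30NOV2023) cite protocol version 1.0 and record no amendment, and the planned study period ran from Q2 2022 to Q3 2023.

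**Working it through.** **Text comparison**

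| Place | Visit covered | Pain | Urgency | QoL |
|---|---|---|---|---|
| Protocol 6.1 | Baseline | yes | yes | yes |
| Protocol 6.3 | End of treatment / week 12 | yes | yes | yes |
| Protocol 6.5 | Early termination | yes | yes | yes |
| **Protocol 6.4** | **Month 6** | **yes** | **not named** | **not named** |
| Table 0-1 footnote 7; SAP 4.8 footnote 7 | Includes month 6 | yes | yes | yes |
| Protocol 7.1.3 to 7.1.3.3 | Includes month 6 | yes | yes | yes |
| Protocol 2.2.2 and 8.3.6; SAP 3.2.2 and 7.2 | Includes month 6 | yes | yes | yes |

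Section 6.4 is the only outlier. SAP 7.2 plans 3 scales × 2 time points = 6 change-from-baseline effects. If every site followed 6.4 literally, 4 of the 6 would have data, and the month-6 effects for urgency and QoL would have none.

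**Size of a partial loss**

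The plan gives no figure to reproduce here, so these are scenarios.

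Inputs from the documents:
- 74 patients with an allowance of 7 dropouts (Protocol 8.1, SAP 5.1), so N = 74 − 7 = 67.
- About 15 sites, with at most about 15 patients each (Protocol 3.1). The average is 67/15 = 4.5 per site, taken as 5.

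Assumptions:
- All 67 have a week-12 value and would reach month 6. The 7 dropouts in SAP 5.1 are those before week 12, so 67 is a best case for month 6.
- Missingness is unrelated to outcome.
- The correlation r between week-12 and month-6 change is not given; I take 0 to 0.7.

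The SAP model has an unstructured covariance, so the month-6 mean borrows from week 12. With L month-6 values lost and m = 67 − L observed, its variance is proportional to (1 − r²)/m + r²/67, against 1/67 with complete data. The confidence-interval width ratio is therefore

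√(67 × [(1 − r²)/m + r²/67]) = √((1 − r²) × 67/m + r²).

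| Scenario | L | m | Share lost | r = 0 | r = 0.7 |
|---|---|---|---|---|---|
| One average site | 5 | 62 | 5/67 = 7.5% | √(67/62) = 1.040 | √(0.51 × 1.0806 + 0.49) = 1.020 |
| One site at the cap | 15 | 52 | 15/67 = 22.4% | √(67/52) = 1.135 | √(0.51 × 1.2885 + 0.49) = 1.071 |
| Two sites at the cap | 30 | 37 | 30/67 = 44.8% | √(67/37) = 1.346 | √(0.51 × 1.8108 + 0.49) = 1.189 |

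The capped-site rows assume no dropout at the affected sites. If dropout is instead spread evenly:
- One capped site is 15/74 = 20%. The ratio is √(74/59) = 1.120 at r = 0 and √(0.51 × 1.2542 + 0.49) = 1.063 at r = 0.7.
- Two capped sites are 30/74 = 41%. The ratio is √(74/44) = 1.297 at r = 0 and √(0.51 × 1.6818 + 0.49) = 1.161 at r = 0.7.

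**The case against.** Section 6.4 omits the two scales but does not exclude them. The introduction to section 6 tells the reader "For details and timings of assessments, refer to" Section 7.0 and Table 0-1, and both carry the full requirement. Sites are trained on the protocol and eCRF and are centrally monitored (9.5), paper questionnaires are collected and entered (9.13), and preassigned data checks raise queries (9.6.1). A query could correct a site before its next patient. Nothing in the documents says how many follow-ups were remote or that any site used 6.4 alone, and a site notice could have clarified the point without an amendment. All analyses are exploratory. SAP 5.0 already provides counts of missing values and individual listings, in which the pattern could be seen.

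Much of this stands. A drafting slip is the likely explanation, loss is not demonstrated, the loss scenarios are hypothetical, and the stakes are two secondary results at one time point. It does not remove the contradiction. Pointing from one passage to another that conflicts with it does not reconcile them, and the documents do not say that VAS completeness is a programmed check. The planned missing-data sensitivity work in SAP 7.1 concerns the primary endpoint, and the early-termination subgroup in SAP 7.3 concerns week 12, so neither covers this pattern.

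**Conclusion.** The concern holds: 6.4 is wrong as written and should be fixed. Confidence is high on the contradiction, which is plain in the text. Whether data were lost cannot be judged without the eCRF (V 0.4 is cited in SAP 11.0) and the questionnaires.

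Exposure is confined to the month-6 changes in urgency VAS and QoL VAS. Each stays estimable as long as some sites collected that scale at month 6. Under the stated assumptions, the loss of precision runs from slight (one average site) to material (two capped sites). Whether dropout is counted inside or outside the affected sites shifts these figures by only a few percentage points. Non-random loss by site could also bias the results, and the width ratios do not capture that. The primary PGA endpoint, all week-12 VAS results, and the month-6 PGA, BPIC-SS and pain VAS are unaffected.

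**What to change.** Reword the VAS line in 6.4 so that, like 6.3 and footnote 7, it names bladder pain, urinary urgency and QoL.

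- **If any patient has still to reach month 6:** notify sites, and check that the month-6 eCRF page and both the on-site and postal questionnaires carry all three scales.
- **If collection is complete**, which is plausible because the SAP postdates the planned end of study: add to SAP 7.2 a by-site table of observed and missing counts for each month-6 VAS. Include the number of patients with pain present but urgency and QoL missing, which is the pattern 6.4 would produce. Report any such loss as a limitation of the two month-6 results.

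The cost is a one-line protocol correction and a site notice, or one extra table built from counts and listings the SAP already plans. No assessment is added beyond the existing schedule.
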